11.1. Primary Analysis: All-Cause Mortality, AESI and SAEs

The primary analyses will be performed for both the on-treatment and on-study periods, as defined in Section 9.1. The primary interest is in the on-treatment period, with the on-study considered an important supportive analysis.

The primary analyses for the on-treatment period will be repeated for subgroups as defined in Section 8.3. Follow-up adjusted summaries (i.e. subject incidence rate/event incidence rate) will not be included in subgroup tables.

An overall Double Dotplot for the percentage of subjects with an event will be provided for mortality and other AESIs for the on-treatment period. This is a panel display with two associated dot-plots; the left-hand panel will show the percentage of subjects with an event in each arm. The right-hand panel will show the difference in percentages, with bars for the 95% confidence interval around the difference. All AESIs and mortality will be displayed on the same plot. Further detail on methodology is given in Section 11.1.1 and Section 11.1.2.

An overall Double Dotplot for exposure-adjusted subject incidence rate will be provided for mortality and other AESIs for the on-treatment period. This is a panel display with two associated dot-plots; the left-hand panel will show the exposure-adjusted subject incidence rate in each arm. The right-hand panel will show the difference in the exposure-adjusted subject incidence rate, with bars for the 95% confidence interval around the difference. All AESIs and mortality will be displayed on the same plot. Further detail on methodology is given in Section 11.1.1 and Section 11.1.2.

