9.2. GSK Adjudication of Death Categories and AESI

See [Appendix 6: PSAP Sections for AESI Reporting](#) for sections of the PSAP relating to death categories and AESI adjudication.

All fatalities (reported during the Week 52 study period) will be identified in the clinical database and subsequently adjudicated by the GSK SRT into a general category of death.

AESI are identified per the preferred terms and other criteria described in [Appendix 6: PSAP Sections for AESI Reporting](#). Malignancies, serious post-infusion systemic reactions, potential opportunistic infections, suicidality and fatalities are adjudicated at the subject level by the GSK SRT. The adjudication occurs prior to database release and is performed for reporting purposes. Final confirmation of adjudications is required before database freeze (DBF).

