11. PRIMARY AND OTHER SAFETY ANALYSES

AESI are defined endpoints in the protocol (and clarified in Section 2.2.3). There are also AESI defined in the Benlysta PSAP (Section 15 and Section 16; see Appendix 6: PSAP Sections for AESI Reporting), which overlap with the protocol-defined AESIs.

Analyses and summaries described in Section 11.1.2 will use the protocol-defined AESIs. All safety data from the AE dataset will be displayed in summaries described in Section 11.2.1. This is expected to cover protocol-defined AESIs and SAEs and additionally, though not anticipated, any non-serious AEs which were not in scope for collection in the protocol but remained on the database at database release. The required PSAP summaries for AESI are described in Section 11.2.4.

The primary study summaries will be of overall subject incidence rates of all-cause mortality and AESIs during the on-treatment period, with supportive summaries during the on-study period. SAEs will be descriptively summarized during the on-treatment and on-study periods.

Safety will also be reported using more detailed summaries of deaths, AESIs (per PSAP), and standard summaries of SAEs. Since there is targeted collection of AEs in the study i.e. AESIs and SAEs, this will be clarified where applicable.

To allow comparison with other studies in the Benlysta program, the format and content of the more detailed AESI summaries will be per PSAP standards. Therefore, data on the primary safety endpoints may be contained both at a high level within Section 11.1 and in more detail in Section 11.2.

Safety analysis will be performed on the As-Treated population.

The extent of missing follow-up data (i.e. for subjects who have withdrawn from the study prior to the Week 52 visit) and off-treatment data will be summarized by treatment group. Exploratory analyses may be performed to characterize the potential impact of off-treatment and missing data on the primary mortality endpoint results (see Appendix 7, Mortality Missing Data Exploratory Sensitivity Analyses).

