11.2.2. Deaths and Serious Adverse Events

In addition to the tabular summaries of AESIs and SAEs described in Section 11.2.1, listings for all SAEs, all fatal SAEs (deaths) and all non-fatal SAEs will be produced. A listing of reasons for considering an AE as an SAE will be provided. The categorization of the cause of death will be adjudicated by GSK (see Section 9.2).

A summary of deaths (fatal SAEs) by category and preferred term will be produced based on the start date of the fatal SAE (to determine whether the event occurred during the relevant study period). A separate summary will be produced of deaths by category and preferred term based on end date of fatal SAE (i.e. using date of death to determine whether the event occurred during the relevant study period). Both summaries will be for the on-treatment period.

Survival status will also be summarized at Week 52, based on information collected on the Week 52 Survival form, for all subjects in the As-Treated population. The number and percentage of subjects will be summarized for each of the following categories:

- Alive
- All Deaths (based on date of death)
 - Deaths on Treatment (during the on-treatment period)
 - Deaths Post-Treatment (after the on-treatment period)
- Unknown
 - Lost to Follow-Up
 - Unattainable

A listing of survival status at Week 52 will also be presented.

11.2.3. AESIs and SAEs Leading to Discontinuation of Investigational Product or Withdrawal from Study

In addition to the tabular summaries described in Section 11.2.1, the following listings will also be produced:

- all AESIs and SAEs leading to premature discontinuation of study agent.
- all AESIs and SAEs leading to withdrawal from the study (i.e., withdrawal of consent).

Note that non-serious AEs leading to withdrawal that are not protocol-defined AESI are not collected in the database.

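### Do the on-treatment-only dot plots, subgroup tables and deaths-by-category summaries leave the 1-year mortality and malignancy objective unanswered?

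*SAP*

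**What the plan says.** The objective in Protocol Section 2 and Week 52 RAP Section 2.1 covers mortality and AESI through 52 weeks. Protocol Section 7.2.1 collects AESI to Week 52 whether or not study agent has been stopped. RAP Section 9.1.1 ends the on-treatment period at the last dose plus 28 days. For mortality and malignancy, the on-study period can run to study Day 372.

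Section 11.1 covers both periods: "The primary analyses will be performed for both the on-treatment and on-study periods, as defined in Section 9.1". It then ranks them: "The primary interest is in the on-treatment period, with the on-study considered an important supportive analysis". The opening of Section 11 agrees on the order, saying that the "primary study summaries will be of overall subject incidence rates of all-cause mortality and AESIs during the on-treatment period, with supportive summaries" for the on-study period.

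Three kinds of display use the on-treatment period alone:

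- **Dot plots.** "An overall Double Dotplot for the percentage of subjects with an event will be provided for mortality and other AESIs for the on-treatment period". The second plot, of exposure-adjusted rates, has the same limit.
- **Subgroups.** "The primary analyses for the on-treatment period will be repeated for subgroups as defined in Section 8.3". Section 8.3 says the same.
- **Deaths by category.** Section 9.2 has a wide scope: "All fatalities (reported during the Week 52 study period) will be identified in the clinical database and subsequently adjudicated by the GSK SRT". Section 11.2.2 plans one category summary by start date of the fatal SAE and one by date of death, and adds: "Both summaries will be for the on-treatment period".

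The survival-status table in Section 11.2.2 nevertheless has a separate row for "Deaths Post-Treatment (after the on-treatment period)".

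**The concern.** A subject who stops in month four and dies in month nine has died within the objective's 1-year horizon. In the on-treatment percentage, whose denominator is all treated subjects (Section 8), that subject counts as having no event. Stopping may be related to prognosis, so ending follow-up there could be informative, in a direction nobody can know beforehand. The dot plots are likely to be the most-read comparison of the arms, and they would show only the while-on-treatment answer. The date-of-death category table would not add up to all first-year deaths, although all of them are adjudicated.

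Two pieces of wording add to the impression. Appendix 7 (Section 15.7.1.1) treats discontinuation as having no bearing on the main estimand, although it sets the end of each subject's window. Section 2.2.3, which lists departures from the protocol analysis, does not mention the choice of period.

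**Working it through.** **1. The plan's own precision figure.** Half-width = 1.96 × √(2p(1−p)/n per arm).

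- Original design, p = 0.68%, n = 2,500: 0.456%.
- Revised design, p = 0.564%, n = 2,000: 0.464%.

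Both round to the ±0.46% in RAP Section 5.1.

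**2. Whose follow-up is lost.** With the first dose on Day 1, the Week 48 dose falls on Day 337, and 337 + 28 = Day 365. Completers lose essentially nothing. A last dose at Week 24 (Day 169) closes the window on Day 197, leaving 168 of 365 days (46%) outside. A last dose at Week 4 (Day 29) closes it on Day 57, leaving 308 days (84%) outside. The issue therefore concerns early stoppers only.

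**3. How many deaths.** The documents give no stopping rate, so this step rests on assumptions. Spread the last dose of early stoppers evenly over the 13 dosing visits from Day 0 to Week 44. The days outside the window sum to 2,506, so the mean share of the year outside is 2,506 / 13 / 365 = 0.528. Let s be the proportion stopping early, f = 0.528s the share of person-time outside, and r the hazard ratio outside versus inside. The share of deaths outside is fr / (fr + 1 − f). Expected first-year deaths are 4,000 × 0.00564 = 22.6.

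| s | r | f | Share of deaths outside | Deaths outside |
|---|---|---|---|---|
| 10% | 1 | 0.053 | 5.3% | 1.2 |
| 10% | 3 | 0.053 | 14.3% | 3.2 |
| 30% | 1 | 0.158 | 15.8% | 3.6 |
| 30% | 3 | 0.158 | 36.1% | 8.1 |

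**4. Effect on the difference.** One death in one arm is 1/2,000 = 0.05 points. With no treatment effect and equal stopping, the on-study and on-treatment differences disagree by chance with SD √(deaths outside)/2,000. That is 0.055 points for 1.2 deaths and 0.143 points for 8.1.

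For an unfavourable asymmetric case, assume 20% stopping with exponential stopping times, a base hazard of 0.5% per year, and a threefold hazard after the last dose in one arm only. The difference is then 0.110 points on-study and 0.015 on-treatment, a gap of 0.095. All of these are well below 0.46.

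**5. Where the later events are shown.** Setting the RAP sections side by side:

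- **Main comparison.** Section 16.3 lists on-study mortality (Table 2.03) and on-study protocol-defined AESI (Table 2.06) as headline results. Sections 11.1.1 and 11.1.2 give both periods the same interval method.
- **Timing.** The Kaplan-Meier figure (Figure 2.04 on-study) and the cumulative deaths by visit cover both periods.
- **Cause.** Table 1 in Section 11.2.1 gives fatal SAEs by SOC and PT on-study as well. The category summary based on SAE start date keeps a late death whose fatal event began inside the window. Only a death whose fatal SAE also began after the window is missing from both category tables.
- **Accounting.** The survival-status table splits all deaths into on-treatment and post-treatment. The date-of-death category table corresponds to the first part. Section 11.2.2 also lists every fatal SAE.
- **Informative stopping.** Sections 10.1 and 11 summarise off-treatment and missing follow-up. Section 15.7.1.2 defines the while-on-study estimand. Section 15.7.1.3 describes a treatment-policy sensitivity analysis whose model has terms for arm, on/off-treatment status and their interaction.

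Malignancies are affected only in the dot plots and subgroup tables, and Table 2.06 shows them on-study.

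**The case for a change.** The strongest case for a change is that the trial went to great lengths to learn vital status at Week 52, including searches of public records, and sized itself on a first-year rate. An on-study dot plot or category table needs only a different period flag. Without them, a reader who looks at the figures alone sees the narrower question, and a few adjudicated deaths get no line in a cause table.

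Part of this stands. In the RAP text supplied, those displays have no on-study version, and the discontinuation sentence in Section 15.7.1.1 is loose. Neither point alters an estimate. The missing entry in Section 2.2.3 is at most an unlisted clarification. Protocol Section 8.5.2 sets no period for the rate difference, and RAP Sections 9.1.1, 11 and 11.1 all say which period leads.

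Giving the two periods equal rank is a different matter. While-on-treatment is a defensible safety estimand. On-study time includes time off drug and possibly commercial belimumab (Section 10.4), which may dilute a difference. The Years 2 to 5 RAP states that the Week 52 data were unblinded on 2 January 2019 and have been reported, so a new ranking now would be a post hoc change of hierarchy. On-study subgroup tables would spread a handful of extra deaths over many strata, where Section 8.3 already expects low incidence.

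**Conclusion.** No change follows. The three display types are confined to the on-treatment period, and first-year events more than 28 days after the last dose are missing from them, subject to the start-date exception. The 1-year question is still answered among the headline results with the same interval method, and off-treatment follow-up is accounted for by arm. Extra displays would change no estimate or conclusion. Putting the on-treatment period first is a fair trade-off that the RAP states openly.

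On the assumed 10-30% stopping and one- to threefold hazard, about 1 to 8 of 22.6 deaths are affected, and the scenarios move the difference by roughly 0.05 to 0.15 points against a half-width of 0.46. Those inputs are assumptions, and no comparable figure can be derived for malignancies.

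The RAP Addendum and the display shells were not available and may already hold some of these outputs. If a reader wants post-treatment deaths by category, the adjudicated categories exist for all Week 52 fatalities, and an analyst can tabulate them as a labelled post hoc display without amending the plan.

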11.1.1. All-Cause Mortality

See Section 11.2.1 and Section 11.2.2 for further summaries and listings of deaths.

Percentages

A summary of the number and percentage of subjects who have died will be provided for belimumab and placebo as well as the difference in the percentage of subjects between the belimumab and placebo groups. The difference in percentages will be evaluated with a 2-sided 95% CI, using the simple asymptotic Chi-Square (Pearson) method [Newcombe, 1998]. This will be considered as the primary method of assessment of the treatment difference.

Subject Incidence Rate

Whilst a difference between belimumab and placebo groups in IP exposure and overall study duration (to Week 52) is not anticipated, to account for this, supplemental summaries using subject incidence rates will be provided.

The subject incidence rate of mortality per 100 subject years will be provided for belimumab and placebo as well as the difference between belimumab and placebo with 95% CIs. For within-group rates per 100 subject years, the 95% CI will be obtained via

on an exact Poisson method [Stokes, 2012]. For differences in rates between groups, the 95% CI will be constructed using a Normal approximation (Wald's method, [Liu, 2006]).

See Section 9.5.14 for further details on the calculation of incidence rates for the on-treatment and on-study periods.

Kaplan-Meier Figure

A plot of the Kaplan-Meier curve, including standard error bands, for all-cause mortality for belimumab and placebo will be provided to show the change in risk over time. The Kaplan-Meier estimates table will be outputted for quality control purposes but will not be used included in the tables or listings.

Time to Event is defined for the On-Treatment Period and On-Study Period as follows:

- For subjects who died during the evaluation period of interest (i.e. on-treatment or on-study): Time to event is the date of death - first exposure date + 1.
- For subjects who did not die or died after the end of the evaluation period of interest (i.e. on-treatment or on-study): Time to event (censored) is the censoring date – first exposure date + 1.

Occurrence and date of death will be determined based on the AE dataset where outcome = fatal (date of death will be derived as the end date of the SAE with fatal outcome).

The censoring date will be assigned based on the evaluation period of interest as follows:

- **On-treatment:** end date for On-Treatment period (see Section 9.1.1)
- **On-study:** end date for On-Study period for mortality and malignancy events (see Section 9.1.1)

The time to event will be calculated in days, as described above. However, the x-axis of the KM plot will display time in weeks. The following conversion will be applied for time to event days to weeks, in order to display the correct week according to the scheduled visit plan (see Section 9.5.2). For example, Day 57 as Week 8, Day 113 as Week 16.

$$\text{Time to event (weeks)} = [\text{Time to event (days)} - 1] / 7$$

The number of subjects at risk at certain timepoints [i.e. Week 8 (Day 57), Week 16 (Day 113), etc.] will be presented for each treatment group. The number of subjects at risk is defined as the number of subjects alive and uncensored at a time just prior to time t (e.g. for Week 8, this would be the number of subjects at risk at the start of Day 57). The Kaplan-Meier plot will be truncated at Week 52.

Cumulative Time to Mortality

The cumulative number and percentage of subjects who died by study visit, derived using visit windows defined in Section 9.5.3, will be displayed by treatment group for the On-Treatment Period and the On-Study Period.

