2.3. Statistical Hypotheses

There are no formal statistical hypotheses for the primary safety endpoints in the study. The main purpose of this study is to provide an evaluation of the difference in the rates of all-cause mortality and all prespecified AESI between the belimumab and placebo groups with a 2-sided 95% CI. SAEs will be summarized descriptively only. See Section [11.1.2](#) for details of the protocol-defined AESIs.

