8.3. Examination of Subgroups

Since the reported incidence for primary safety endpoints is expected to be low, subgroup categories may be refined where necessary.

Mortality, AESIs and all AEs (i.e. AESI and SAEs) during the On-Treatment period will be summarized by the following subgroups:

- Age (<65 years vs. ≥ 65 years)
- Gender (Male vs. Female)
- Race Stratification (Black vs. Other). The Black category is defined as subjects who are in the race category “Black or African American”. The race hierarchy rule (Section [9.5.10](#)) will not apply and a subject will be categorized as Black if they have selected multiple race categories and any of them is “Black or African American”.
- Randomization Stratification Factors (see Section [8.2](#), derived from eCRF data):
 - Region (US/Canada, Central America/South America/Mexico, Europe/Australia/Israel, Asia)
 - Screening SELENA SLEDAI (≤ 9 , ≥ 10). Note: if any individual item is missing the total score cannot be calculated, however if the subject can be definitively

categorized as ≤ 9 or ≥ 10 regardless of the response to the missing item(s) then the appropriate subgroup will be assigned.

- Steroid dose (≤ 7.5 mg/day, >7.5 mg/day prednisone or equivalent) (baseline average daily dose, see Section 9.5.16.1). Note: Only systemic steroids given for SLE are included in the derivation.
- Screening Complement Levels and Anti-dsDNA (Low Complement and High Anti-dsDNA binding, Not (Low Complement and High Anti-dsDNA binding)), derived from the screening SELENA SLEDAI assessment. This subgroup is intended to be an indicator of high versus low disease activity. Note: If the evaluations to the SELENA SLEDAI assessment questions “Low Complement” and “Increased DNA Binding” are both missing, the subject will not be classified into one of the subgroup categories. If either item is marked “No”, the subject will be classified into the Not (Low Complement and High Anti-dsDNA binding) group regardless of whether the other item is missing or “Yes”.

Demographic and baseline characteristics and baseline disease activity will also be summarized by all subgroups except Screening Complement Levels and Anti-dsDNA.

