11.1.2. Protocol-Defined AESI

Protocol-defined AESIs are defined in Section [9.5.12](#).

Note, for Suicidality (C-SSRS) only, a subject must have at least one pre-treatment C-SSRS assessment (screening and/or baseline) and at least one on-treatment C-SSRS assessment (post-baseline) to be included in the summaries.

Percentages

For each of the AESIs a summary of the number and percentage of subjects experiencing at least one event will be provided for belimumab and placebo as well as the difference in the percentage of subjects (and 95% CI) between the belimumab and placebo groups using the same methodology as for mortality.

Subject Incidence Rate

The incidence rate for each AESI per 100 subject years will be provided for belimumab and placebo groups as well as the difference between placebo and belimumab (and 95% CI) using the same methodology as for mortality.

Event Incidence Rate

The number of events and event rate for each AESI, except Suicidality (C-SSRS), per 100 subject years will be provided for belimumab and placebo groups.

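### The only planned interval for percentage differences collapses to [0, 0] when neither arm has an event, and the subgroup tables carry no other bound

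*SAP*

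**What the plan says.** All references are to the Week 52 RAP in the SAP unless noted.

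- **Method.** Section 11.1.1: "The difference in percentages will be evaluated with a 2-sided 95% CI, using the simple asymptotic Chi-Square (Pearson) method". The RAP calls this the primary way to assess the treatment difference. All three mortality estimands in Appendix 7 use the same formula.
- **Reach.** Section 11.1.2 gives each AESI a percentage difference "between the belimumab and placebo groups using the same methodology as for mortality". The dot plot in Section 11.1 shows these intervals side by side: "All AESIs and mortality will be displayed on the same plot".
- **Subgroups.** Section 11.1: "The primary analyses for the on-treatment period will be repeated for subgroups as defined in Section 8.3". It then adds: "Follow-up adjusted summaries (i.e. subject incidence rate/event incidence rate) will not be included in subgroup tables". The exact Poisson limits for each arm's rate therefore appear in the overall tables but not in the subgroup tables.
- **Sparse data.** Section 8.3: "Since the reported incidence for primary safety endpoints is expected to be low, subgroup categories may be refined where necessary". Section 8 says that a zero count is shown without a percentage. Neither section says what interval to show when both counts are zero.
- **Role of the interval.** Section 2.3 sets no hypothesis test. The study's purpose is to evaluate each difference "between the belimumab and placebo groups with a 2-sided 95% CI".

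**The concern.** With no test, the interval is the result. In a safety trial I expect readers to look mainly at the upper limit, to see how large an excess on belimumab remains possible. That is my reading, not wording from the plan.

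The simple asymptotic standard error is built from the observed proportions, so it is zero when both are zero. A subgroup row with no events in either arm would then show no uncertainty at all, however small the subgroup. If the row is left blank, the reader gets no bound. The RAP foresees low incidence and removes the rate summaries from these tables, so nothing else there supplies one.

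**Working it through.** **Inputs.** Mortality 6/1,190 = 0.504% (placebo) and 14/2,484 = 0.564% (belimumab), from Section 5.1; 2,000 per arm, from 4,000 randomised 1:1. The documents give no subgroup sizes, so 50 to 500 per arm is an assumed range.

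**1. The plan's own figure.** Half-width = 1.96 × √[2p(1−p)/n].
- p = 0.68%, n = 2,500: 0.456 points.
- p = 0.564%, n = 2,000: 0.464 points.

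Both round to the stated ±0.46%. A continuity correction would give 0.496 and 0.514, so the planned interval is the uncorrected one.

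**2. Full trial.** I enumerated two independent binomials exactly, at 0.564% vs 0.504% and 2,000 per arm. Call it a harm-side miss when the whole interval lies below the true excess (nominal 2.5%). The harm-side miss is 2.7% and two-sided coverage is 94.8%.

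**3. The 0 vs 0 cell.** The planned interval is 0 ± 1.96 × √(0 + 0) = [0, 0] at any n. The Newcombe interval reduces here to ±z²/(n + z²), with z² = 3.84. At n = 100 this is 3.84/103.84 = 3.7 points. The chance of the cell is (1−0.00564)ⁿ(1−0.00504)ⁿ.

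| Per arm (assumed) | P(0 vs 0 deaths) | Planned interval | Newcombe, points |
|---|---|---|---|
| 50 | 59% | [0, 0] | ±7.1 |
| 100 | 34% | [0, 0] | ±3.7 |
| 200 | 12% | [0, 0] | ±1.9 |
| 300 | 4% | [0, 0] | ±1.3 |
| 400 | 1% | [0, 0] | ±1.0 |

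**4. Other cells.** Here 0 vs 0 is set aside. The doubled scenario is 12/1,190 vs 6/1,190, a true excess of 0.504 points. All entries are harm-side misses; Newcombe's is for the doubled scenario.

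| Per arm (assumed) | Planned, mortality doubled | Planned, 0.564% vs 0.504% | Newcombe, doubled |
|---|---|---|---|
| 50 | 0.01% | 0.01% | 0.0% |
| 100 | 0.5% | 0.10% | 0.1% |
| 150 | 3.9% | 0.3% | 0.2% |
| 200 | 8.5% | 0.64% | 0.3% |
| 300 | 4.8% | 1.37% | 1.2% |
| 400 | 4.1% | 1.95% | 1.0% |

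At 500 per arm and the documents' rates the planned interval's miss is 2.29%, still below nominal.

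The onset has a simple cause: it is set by cells with no belimumab deaths and at least one placebo death. At 150 per arm, 0 vs 2 deaths gives an upper limit of −1.333 + 1.96 × √(0.01333 × 0.98667/150) × 100 = 0.502 points, just below 0.504. At 200 per arm, 0 vs 1 gives −0.500 + 0.978 = 0.478 points, also below. At 100 per arm, 0 vs 1 gives 0.95 points, which covers the excess.

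**The case against.** The case against is substantial, and part of it stands.

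- **The full-trial interval is sound.** Agreed. It covers mortality adequately and matches the sample-size method. A reader might infer that the main mortality result is unreliable; step 2 shows otherwise.
- **The upper limit is not too low in every small subgroup.** Agreed. It is tempting to say that any true excess makes the upper limit too low wherever data are sparse. Once 0 vs 0 is set aside, the miss is far below 2.5% at 50 and 100 per arm even with mortality doubled. At the documents' own rates it stays below 2.5% up to 500 per arm.
- **[0, 0] may never be printed.** The RAP does not say that it will be. Suppressing the percentage for a zero count is compatible with a blank row, and the display shells were not supplied. Including the 0 vs 0 cell, the harm-side miss with mortality doubled is 46.8% at 50 per arm and 22.4% at 100, but almost all of that is this one cell, and it counts only if [0, 0] is shown. A blank removes the false precision but still leaves no bound.
- **Categories may be refined.** This could merge the smallest cells. It is optional, has no stated rule and leaves the formula unchanged.
- **Subgroups are secondary, and Week 52 is already reported.** True. This limits the severity and means that any addition must be labelled post hoc.
- **The RAP Addendum may cover it.** Possible. The Years 2 to 5 RAP (Section 1) says that it adds safety analyses, but it was not supplied.

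**Conclusion.** The concern holds in a limited form and is worth considering; it is not a defect in the primary result. In the supplied documents the only interval for a percentage difference is the simple asymptotic one. With no events in either arm it shows no uncertainty, and no supplied text changes this or gives the reader of a subgroup table a bound. At the trial's planning mortality rates such a cell has about a one-in-three chance at 100 per arm, where an excess of up to 3.7 points remains compatible with the data (Newcombe).

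The lesser fault, an upper limit that falls too low in cells other than 0 vs 0, is shown here for mortality about doubled, from about 150 per arm: 3.9%, 8.5%, 4.8% and 4.1% at 150, 200, 300 and 400, against 2.5%.

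The conclusions rest on assumed subgroup sizes, on equal arms within a subgroup, and, for the lesser fault, on an assumed doubling that no document predicts. The [0, 0] result follows from the formula alone.

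**What to change.** Keep the prespecified interval as primary, and leave the planned dot plot as it is. Add a Newcombe hybrid score interval for the percentage difference to the subgroup tables and to any AESI row with few events. Label it supplementary and post hoc, because the Week 52 data were unblinded on 2 January 2019 and have been reported. State one display rule: a 0 vs 0 cell shows the Newcombe interval, never [0, 0] or a blank.

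The cost is one extra column computed from existing counts; no new data are needed. The trade-off is conservatism: in the doubled-mortality scenario, Newcombe's harm-side miss is at most 1.2% at the sizes tabulated up to 400 per arm, below the nominal 2.5%, so the intervals are wider than strictly needed. If the RAP Addendum or the display shells already provide such an interval and rule, nothing further is required.
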